3.0 Study Design

General study design

This study is a phase 1, randomized, double-blind, placebo-controlled study of four dose cohorts. The study will enroll and randomize a total of 50 healthy subjects from five study sites to receive an intramuscular (IM) injection of either ADM03820 or placebo. Five dosing cohorts will be enrolled sequentially. Dose escalation will occur after the Safety Review Committee (SRC) reviews safety data and confirms that the dose escalation criteria are met. Within each cohort, 8 actives and 2 placebos will be included. The 5 dosing cohorts are

- 1. Cohort 1 –150 mg IM injection (8 active, 2 placebo)
- 2. Cohort 2 300 mg IM injection (8 active, 2 placebo)
- 3. Cohort 3 300 mg IM injection (8 active, 2 placebo)
- 4. Cohort 4 300 mg IM injection (8 active, 2 placebo)
- 5. Cohort 5 600 mg IM injection (8 active, 2 placebo)

All enrolled subjects in Cohorts 1 and 2 will follow the study schedule below:

- Screening (Day -14 to Day -2)
- Baseline/admission to Unit (Day -1)
- Dosing (Day 1)
- Discharge and outpatient follow-up (Day 2 to Day 540)

[figure not shown]
According to Protocol v7.0, subjects in Cohorts 3, 4 and 5 will be admitted to the unit the day of the planned dosing. Thus, study schedule is specified below:

- Screening (Day -14 to Day -2)
- Dosing (Day 1)
- Discharge and outpatient follow-up (Day 2 to Day 540) for Cohorts 3 and 4
- Discharge and outpatient follow-up (Day 2 to Day 379) for Cohort 5

A schematic of the study design is summarized in Figure 1.

Figure 1 - Schematic of Study Design

Randomization procedures

This is a Phase 1 double-blinded, placebo-controlled trial that will randomize subjects within five dosing cohorts to either active or placebo.

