7.0 Statistical Methods

General statistical conventions

All statistical procedures will be completed using SAS version 9.4 (or higher), R version 4.0.0 (or higher), or Phoenix WinNonLin 8.3.1 (or higher).

Unless otherwise stated, all statistical testing will be two-sided and will be performed using a significance (alpha) of 0.05. Two-sided 95% confidence intervals (CI) will be provided when relevant.

Continuous variables will be summarized using descriptive statistics, including number of subjects (n), mean, median, standard deviation (SD), interquartile ranges (IQR), minimum, and maximum.

For categorical variables, summaries will include counts of subjects and percentages. Percentages will be rounded to one decimal place.

For summary purposes, baseline will be defined as the last available pre-dose value. All summaries will be presented by treatment group, unless otherwise specified.

All subject data, including those derived, will be presented in individual subject data listings. Unless otherwise stated, unscheduled visit results will be included in date/time chronological order, within patient listings only. All listings will be sorted by subject ID, date/time and visit. The treatment group will be stated on each listing. Unless otherwise stated, data listings will be based on FAS.

Unscheduled data points will not be used in any summary tables separated by visit but will be presented in each listing as appropriate.

Subject disposition

Subject disposition information will be summarized by dosing cohort, treatment group and overall. The number and percentage of subjects who are enrolled, who complete the study, and who withdraw early from the study will be presented.

The primary reasons for early withdrawal will also be tabulated, including withdrawal by subject, physician decision, lost to follow-up, major protocol deviation or other.

The number of subjects enrolled will be used as the denominator for the percentage calculation. Subject disposition will be listed.

The number and percent of subjects in each analysis set will also be tabulated. A listing of each subject excluded from an analysis population will be listed as well as the reason why they were excluded from the population.

Treatment Misallocations: if a subject is

- Randomized but withdrawn prior to dosing, then they will be replaced and will not be included in any analysis.
- Randomized but receive incorrect treatment, they will be reported under the treatment they actually

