8.6.5 Analysis of secondary efficacy endpoint(s)

Secondary efficacy analysis will be based on microneutralization assay and immunogenicity/ADA assay using blood samples drawn at various predetermined visit days using per-protocol population.

Pharmacokinetic (PK) and Log-Transformed Pharmacokinetic (PK) Parameters will be summarized descriptively by treatment group.

Microneutralization titers will be summarized descriptively by treatment group and compared among treatment groups using Kruskal-Wallis test on log scale. GMT of ADA and GMFR over the initial GMT at baseline will be summarized descriptively by treatment group and compared using Kruskal-Wallis test among cohorts at each study visits. Exploratory pairwise comparisons will also be conducted using Wilcoxon rank sum test; however, resulting p-values will not be corrected for multiplicity. Microneutralization titers on log scale and GMTs for ADA will be plotted by treatment group over study days.

Incidence of the first case of SARS-CoV-2 RT-PCR positive symptomatic illness occurring after dosing through Day 365 will be summarized descriptively by treatment group. Incidence of SARS-CoV-2 RT-PCR

positive severe or critical symptomatic illness occurring after dosing through Day 365 will be summarized descriptively by treatment group.

Incidence of COVID-19 related Emergency Department visits occurring after dosing through Day 365 will be summarized descriptively by treatment group.

Due to the small number of subjects in this study, negative hypothesis tests should be interpreted carefully as the study has not been powered to detect differences between groups.

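### The planned Kruskal-Wallis tests for MN and ADA do not isolate dose: placebo subjects are not excluded, dose order is ignored, and the pairwise tests that could address dose are not named

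*SAP*

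**What the plan says.** The secondary objective (SAP 2.0) is the PK and immunogenicity of different doses. SAP 3.0 lists one cohort at 150 mg, three at 300 mg and one at 600 mg, and states: "Within each cohort, 8 actives and 2 placebos will be included".

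SAP 8.6.5 uses the per-protocol population, which SAP 5.0 defines as randomized subjects free of major violations, so placebo recipients stay in. There:

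- MN titres are "compared among treatment groups using Kruskal-Wallis test on log scale".
- ADA GMT and fold rise are summarized by treatment group but "compared using Kruskal-Wallis test among cohorts at each study visits", so the summary and the test use different labels for the groups.
- For the follow-up tests the SAP states: "Exploratory pairwise comparisons will also be conducted using Wilcoxon rank sum test; however, resulting p-values will not be corrected for multiplicity". The pairs are not listed.
- The closing caution is that "negative hypothesis tests should be interpreted carefully as the study has not been powered to detect differences between groups".

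SAP 7.0 adds that "all statistical testing will be two-sided and will be performed using a significance (alpha) of 0.05". Neither document defines *treatment group*. No trend test or dose-response estimate is planned for MN or ADA.

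**The concern.** A reader of the study report will want to know whether neutralization or ADA changes between 150, 300 and 600 mg. The omnibus tests answer other questions. A significant MN result may mean only that drug differs from saline. A non-significant ADA result may partly reflect untreated subjects in every group and degrees of freedom spent on three cohorts at one dose. The SAP's interpretive caution covers negative results, yet the MN test is easiest to misread when it is positive.

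**Working it through.** **The plan's own figures.** SAP 4.0 gives 0.728 to 0.996 for at least one event in 8, and an upper bound of 0.369 for 0/8. Both reproduce: 1 − 0.85^8 = 0.7275, 1 − 0.5^8 = 0.9961, 1 − 0.025^(1/8) = 0.3694. They concern toxicity. The documents give no power, SD or effect size for MN or ADA, so those below are assumptions.

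**Inputs from the documents.** Five cohorts of 8 active and 2 placebo: 40 active (8 at 150 mg, 24 at 300 mg, 8 at 600 mg) and 10 placebo. Two-sided alpha is 0.05.

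**1. MN with placebo as a group.** Suppose all 10 placebo titres lie at the floor, below all 40 active titres. The overall mean rank is 25.5, the placebo mean rank is 5.5 and the active mean rank is 30.5. H is smallest when the active groups have identical mean ranks:

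H = 12/(50 × 51) × [10 × (5.5 − 25.5)² + 40 × (30.5 − 25.5)²] = 12/2550 × (4000 + 1000) = 23.5

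The critical value is 11.07 for six groups (5 df) and 7.81 for placebo plus three doses (3 df). The test rejects with no dose difference at all, and simulation agrees (100% of runs). If *treatment group* means active versus placebo, this is a two-group test with no dose content.

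**2. Order and scale.** Kruskal-Wallis uses ranks and treats groups as unordered. In a simulated data set p was 0.0130 on the raw scale, on the log scale and after permuting the group labels. The log-scale wording is harmless but has no effect.

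**3. Power for a dose trend in MN, active recipients only.** The trend test is a Jonckheere-type test on 150 < 300 < 600 mg. Units are log2, with 1,500 runs per row. Power depends on the ratio of slope to SD, so natural-log units give the same answers at the same ratio.

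| Slope per doubling | SD | Kruskal-Wallis, 5 cohorts | Kruskal-Wallis, 3 doses | Wilcoxon 150 v 600 | Trend test |
|---|---|---|---|---|---|
| 0.5 | 0.7 | 0.49 | 0.64 | 0.72 | 0.75 |
| 0.5 | 1.0 | 0.24 | 0.35 | 0.45 | 0.48 |
| 0.5 | 1.5 | 0.12 | 0.16 | 0.22 | 0.24 |
| 1.0 | 0.7 | 0.99 | 1.00 | 1.00 | 1.00 |
| 1.0 | 1.0 | 0.82 | 0.92 | 0.95 | 0.97 |
| 1.0 | 1.5 | 0.43 | 0.59 | 0.69 | 0.72 |

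With no dose effect the trend test rejects in 4.7% to 5.7% of runs. A separate set of 4,000 runs at the first row's ratio gave 49% against 77%; with 1,500 runs the Monte Carlo error is about 1 point.

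**4. ADA among cohorts of 8 active plus 2 placebo.** Assumed positivity at 150/300/600 mg, with placebo negative:

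| Positivity | Cohorts with placebo | Active only, 5 cohorts | Active-only trend |
|---|---|---|---|
| 10/30/60% | 0.27 | 0.33 | 0.59 |
| 20/50/90% | 0.40 | 0.54 | 0.79 |

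With equal positivity of 20, 60 or 90% in all cohorts, the mixed test rejects in 3.6%, 1.3% or 0.0% of runs, so it is conservative. Every cohort has the same 2/10 placebo share, so this is dilution and not bias.

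**5. Prior immunity and the 600 mg dose.** Protocol 5.2, exclusions 15 and 24, lets seropositive subjects, and those vaccinated more than 14 days before enrollment, into Cohort 5 only. With no dose effect, SD 0.7 ln and an assumed 0.7 to 1.0 ln of extra titre throughout Cohort 5, an unadjusted active-only trend test rejects in about 43% to 70% of runs. Kruskal-Wallis over the five active cohorts does so in 37% to 71%. Changing the test alone does not solve this.

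**The case against.** The strongest reply is that 8.6.5 already contains a route to dose. A Wilcoxon test of 150 against 600 mg has nearly the power of the trend test (0.72 against 0.75 in the first row). That stands, and the inference that the plan cannot answer the dose question at all is not supported. What remains is that no pair is named. With 10 to 15 uncorrected pairs at one visit, the chance of at least one false positive is 1 − 0.95^10 = 0.40 to 1 − 0.95^15 = 0.54. This treats the pairs as independent and every null as true, and neither is likely to hold. A reader might go further and count the expected false positives over the whole plan. The documents do not fix the groups or the pairs, and the per-visit wording is attached to ADA only, so no such count is supported.

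Second, placebo inclusion is inferred from wording. Protocol 11.3.2 and 11.3.3 list dose cohort and control group separately, so *cohorts* in the ADA sentence may mean active groups, and the table shells are in a separate document. That is fair, and it makes definition the first step. If control were instead a separate ADA group, that test would share the MN problem.

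Third, the certain rejection depends on placebo at the floor. Some Cohort 5 placebo subjects may have prior immunity, and all subjects may be vaccinated after Day 90, before the Day 120, 150 and 180 MN samples. If half the placebo subjects reach active-level titres, rejection falls to about 38%; at 80% it falls to about 8%. Those rejections still say nothing about dose.

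Fourth, contrasts among the 300 mg cohorts are not all wasted: Cohort 4 receives the 100 mg/mL product as one injection, Cohorts 2 and 3 the 50 mg/mL product as two. This stands and argues for keeping the by-cohort summaries.

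Finally, these are unpowered secondary analyses with no stated dose-response hypothesis, and the SAP labels the pairwise tests exploratory and uncorrected. That limits the weight of the point. It does not justify an ill-defined comparison when a better one is cheap.

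**Conclusion.** The point holds in a limited form. As written, the MN omnibus test does not isolate dose under either reading of *treatment group*. The ADA test, read literally, is diluted and conservative. It can still detect cohort differences, at reduced power (0.40 against 0.54 in one scenario), and a reader who inferred bias would be wrong, because the placebo share is equal in every cohort. Both tests ignore dose order.

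That Kruskal-Wallis ignores order, and that MN rejects when all placebo titres lie below all active titres, follow from the ranks alone. The power gains, such as 49% to 77%, are illustrative. They depend on the assumed slope and SD, and nearly vanish at a slope of 1.0 and SD of 0.7 log2 (0.99 against 1.00). The comparator in those figures is Kruskal-Wallis in active recipients, which is more favourable than the literal plan. The primary safety analysis is not affected.

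**What to change.** Amend SAP 8.6.5 as follows.

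- Define *treatment group*, and say whether *cohorts* includes placebo subjects.
- Restrict MN and ADA dose comparisons to ADM03820 recipients. Show pooled placebo as a descriptive reference or in a separate active-versus-placebo comparison.
- Add a two-sided trend test over 150 < 300 < 600 mg, with the geometric mean ratio per dose doubling and its 95% CI, labelled exploratory.
- For MN, adjust for the pre-dose titre or use change from baseline, and give a sensitivity analysis without Cohort 5. Note the post-Day 90 vaccination allowance when reading Days 120 to 180.
- Keep the by-cohort summaries so that the 50 and 100 mg/mL products at 300 mg can be compared.
- Name the Wilcoxon pairs of interest, such as 150 against 600 mg.

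The cost is SAP wording and a few lines of code, with no new samples, since pre-dose MN is already scheduled. There are three limits. A trend test is less sensitive to a non-monotone pattern. Cohorts 1-4 are screened seronegative, so pre-dose titres will vary mainly within Cohort 5 and the baseline adjustment will rest largely on that cohort. Without Cohort 5, only 150 against 300 mg remains. The MN result at 600 mg should therefore be worded cautiously whatever test is used.

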3.2.2. Secondary Endpoints

- The assessment of C_{max} , T_{max} and $AUC_{(0-t)}$ for total antibodies of ADM03820 as measured by enzyme-linked immunosorbent assay (ELISA) for samples from Cohorts 1 and 2. The assessment of C_{max} , T_{max} and $AUC_{(0-t)}$ for each of the monoclonal antibodies of ADM03820 as measured by enzyme-linked immunosorbent assay (ELISA) for samples from Cohort 3, Cohort 4, and Cohort 5.
 - Pharmacokinetic samples will be tested by ELISA at pre-dose, 2, 4, 8, and 24 hours post dose, and on Days 3, 4, 8, 15, 30, 45, 60, 90, 120, 150, 180, and 365 for all cohorts
 - Samples will be tested by Microneutralization at pre-dose and Days 2, 15, 30, 60, 90, 120, 150, and 180 for all cohorts
- Samples will be tested by Electrochemiluminescence Assay (ECLA) to evaluate presence of anti-drug antibodies (ADA) collected for all cohorts.
 - ADA samples will be tested at pre-dose, and Day 15, 30, 45, 60, 90, 120, 150, 180, 365 for all cohorts
- Incidence of the first case of SARS-SoV-2 RT-PCR positive symptomatic illness occurring after dosing through Day 365
- Incidence of SARS-CoV-2 RT-PCR positive severe or critical symptomatic illness occurring after dosing through Day 365
- Incidence of COVID-19 related Emergency Department visits occurring after dosing through Day 365

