7.6.3. Immunogenicity / Anti-Drug Antibody Assay

Six-mL samples of blood will be drawn at pre-dose and on Days 15, 30,45,60, 90, 120, 150, 180, and 365 for determining the presence of ADA using validated ECLA methods that detect anti-mAb2130 and anti-mAb2381 antibodies in serum. This will be done to assess immunogenicity. For each timepoint, aliquot at least 0.50 mL each of serum into three 1.8 mL sterile cryogenic vials, freeze and store serum samples at \leq -70°C until shipment

7.6.4. **RT-PCR Testing for SARS-CoV-2**

A nasopharyngeal swab specimen will be collected for RT-PCR testing for SARS-CoV-2 at screening and upon presentation of COVID-19 symptoms. If a subject acquires COVID-19 during their participation in the study, they should seek and obtain the appropriate treatment.

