11.3.5. Immunogenicity

Immunogenicity will be measured by the development of antibody titers. The presence of ADA will be measured over the course of the post-injection period.

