- Samples will be tested by Electrochemiluminescence Assay (ECLA) to evaluate presence of anti-drug antibodies (ADA) collected for all cohorts.
 - ADA samples will be tested at pre-dose, and Day 15, 30, 45, 60, 90, 120, 150, 180, 365 for all cohorts
- Incidence of the first case of SARS-CoV-2 RT-PCR positive symptomatic illness occurring after dosing through Day 365
- Incidence of SARS-CoV-2 RT-PCR positive severe or critical symptomatic illness occurring after dosing through Day 365

BST1302-SOP-T01/v1.0/2020 Page 14 of 26

Incidence of COVID-19 related Emergency Department visits occurring after dosing through Day 365

Exploratory endpoint(s)

None.

Safety endpoint(s)

No additional safety endpoints besides those specified in Section 4.1.

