5.0 Analysis Populations

Full Analysis Set (FAS)/Intention-To-Treat population (ITT)

An intent-to-treat population will consist of all subjects randomized and will be analyzed as randomized.

Safety population (Safety)

All subjects who received study product will be included in the safety population and analyzed as treated.

Per-Protocol population (PP)

The Per-protocol population will consist of all subjects in the ITT population who were free from major protocol violations. Patients will be included in the analysis according to the treatment group they are randomized to.

Pharmacokinetics (PK) population

The PK population will consist of all subjects who complete ADM03820 injection and have sufficient evaluable PK samples for the estimation of PK parameters. Subjects in the PK population will be analyzed in the dose cohort and treatment group corresponding to the study drug that they have received.

Protocol deviations

Protocol deviation data will be captured in the clinical trial management system. Extracts of all protocol deviations will be reviewed periodically and prior to any interim or final analyses. All protocol deviations and the exclusion of participants from analysis sets will be identified prior to unblinding through clinical review and input provided by the sponsor using supportive participant listings provided by the ICON GPHS statistician based upon data recorded in the clinical trial management system.

Further, deviations from the protocol will be classified as major or minor. Classification of major and minor protocol deviations is determined prior to participant enrollment and is outlined in detail in the protocol deviation criteria documentation managed by the clinical trial management team.

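### The ADA endpoint is presence of anti-drug antibodies, but the SAP text specifies only visit-wise titre summaries in the per-protocol set, with no subject-level ADA status or exposed-subject denominator

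*SAP*

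**What the plan says.** **Endpoint.** Protocol section 3.2.2 has samples tested by electrochemiluminescence assay "to evaluate presence of anti-drug antibodies (ADA) collected for all cohorts". The SAP's secondary endpoint list repeats this and sets the times: "ADA samples will be tested at pre-dose, and Day 15, 30, 45, 60, 90, 120, 150, 180, 365 for all cohorts". That is one pre-dose and nine post-dose samples. Protocol section 7.6.3 describes the draws as being "for determining the presence of ADA using validated ECLA methods that detect anti-mAb2130 and anti-mAb2381 antibodies in serum".

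**Protocol analysis.** Section 11.3.5 has two sentences. The first measures immunogenicity through the development of titres. The second says: "The presence of ADA will be measured over the course of the post-injection period".

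**SAP analysis.** Section 8.6.5 bases the ADA work on assays "using blood samples drawn at various predetermined visit days using per-protocol population". The measures are given as "GMT of ADA and GMFR over the initial GMT at baseline will be summarized descriptively by treatment group", and these are "compared using Kruskal-Wallis test among cohorts at each study visits". Exploratory pairwise Wilcoxon tests and a plot of ADA GMTs over study days complete the list.

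**What is absent.** Table 3 (derived variables, SAP section 6.0) has no ADA variable. The safety analysis section uses all dosed subjects but contains no ADA analysis. The only declared change from the protocol (SAP section 8.0) is the added per-protocol population.

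**The concern.** Immunogenicity is half of the secondary objective, this is a first-in-human antibody product, and protocol section 2.3.1 lists ADA formation as a potential risk. The question a reader will bring is how many dosed subjects developed ADA. A geometric mean titre answers a different question, since it mixes how many subjects respond with how strongly they respond. Tables built one visit at a time cannot show whether the positives at successive visits are the same people.

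The analysis set adds to this. The per-protocol set drops subjects with major violations and groups the rest as randomised. The SAP already has a set based on exposure: "All subjects who received study product will be included in the safety population and analyzed as treated". It is not used for ADA.

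The SAP also gives no value for a negative sample in a geometric mean. The rule for results reported as below a limit, in section 8.7.2, covers only chemistry, hematology and urinalysis.

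**Working it through.** **1. The plan's own figures.** The documents give no ADA rate or titre. The only related figures are the design values for n = 8 active subjects, and they reproduce:
- P(at least one event) = 1 − (1 − p)^8 = 0.7275 at p = 0.15 and 0.9961 at p = 0.5 (stated 0.728 and 0.996).
- Exact two-sided 95% upper bound for 0/8 = 1 − 0.025^(1/8) = 0.369 (stated 0.369).

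**2. Assumptions for the illustrations.** There are 8 active subjects per cohort (from the documents). All are at an assumed floor titre of 5 at baseline and whenever negative. GMT = exp(mean of ln titre) and GMFR = GMT/5. Every titre below is assumed.

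**3. One visit.** GMT = 5 × (titre/5)^(k/8) for k positives.

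| Positives | Titre | GMT | GMFR | Median | Maximum |
|---|---|---|---|---|---|
| 1/8 | 1280 | 5 × 256^(1/8) = 10.0 | 2.0 | 5 | 1280 |
| 2/8 | 80 | 5 × 16^(2/8) = 10.0 | 2.0 | 5 | 80 |
| 4/8 | 20 | 5 × 4^(4/8) = 10.0 | 2.0 | 12.5 | 20 |
| 8/8 | 10 | 5 × 2^(8/8) = 10.0 | 2.0 | 10 | 10 |

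GMT and GMFR do not distinguish these patterns. The median and maximum, which the general conventions in SAP section 7.0 would add, do separate them, but still do not state incidence.

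**4. Across visits.** Put one sample at titre 80 at each of the first eight post-dose visits, with everything else at the floor. Each of those visits then shows:
- GMT 5 × 16^(1/8) = 7.07; GMFR 1.41
- mean (80 + 7 × 5)/8 = 14.4; SD 26.5
- median 5; quartiles 5 and 5; range 5 to 80
- 1/8 positive

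The tables are the same whether the eight positive samples come from:
- 1 subject: 12.5% ever positive (exact 95% CI 0.3 to 52.7)
- 2 subjects: 25% (3.2 to 65.1)
- 4 subjects: 50% (15.7 to 84.3)
- 8 subjects: 100% (63.1 to 100)

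A less extreme case makes the same point. Three subjects each positive at a different visit never exceed 1/8 at any visit, yet the cumulative incidence is 3/8 = 37.5% (8.5 to 75.5).

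**5. Value for negatives.** With one subject at 1280 and seven at f, GMT = f × (1280/f)^(1/8). For f = 1, 5 and 20 this gives 2.4, 10.0 and 33.6, and GMFR (GMT/f) is 2.4, 2.0 and 1.7.

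**6. Analysis set.** No per-protocol exclusion rate is given. If a cohort's only positive subject were excluded, 1/8 (12.5%) would become 0/7, with upper bound 1 − 0.025^(1/7) = 41.0%.

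**The case against.** The other side has four substantial points.

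- **The endpoint wording is sample-based.** It speaks of testing samples at listed visits. The same list uses the word incidence for three COVID-19 endpoints and not for ADA. A reader might infer that the protocol literally asks how many exposed subjects develop ADA; it does not. Subject-level incidence is the natural reading of presence over the post-injection period, but it remains a reading.
- **The titre analysis is legitimate.** Protocol section 11.3.5 names titres first. A reader might infer that section 8.6.5 contradicts the protocol. It does not; it carries out one of the two sentences.
- **Generic conventions narrow the gap.** SAP section 7.0 summarises categorical variables as counts and percentages, and lists all subject data on the full analysis set. If the assay's positive/negative call is in the data, this could give the number positive by visit, and ten rows per cohort could be counted by hand. Neither supplies an ever-positive rule, a treatment of baseline positives or missing samples, or an exposed-subject denominator.
- **The examples are constructed.** The rotating-positives case is extreme. Undosed subjects are already excluded from every analysis, the product is a single dose given by site staff, and the major/minor classification is fixed before enrolment. The loss to the per-protocol set could be zero.

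All four stand as limits on the claim. None of them gives the presence part of the endpoint a subject-level analysis.

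**Conclusion.** The point holds as a gap in the SAP text. For ADA, section 8.6.5 specifies titre-scale measures by visit in the per-protocol set. Followed exactly, those summaries yield no ADA incidence among exposed subjects, and incidence cannot be recovered from them.

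The size is a matter of identifiability. Under assumed titres, one set of visit tables is compatible with anything from 1/8 to 8/8 ever positive. That does not make a reporting error likely, and no figure stated in the documents is wrong on this point. Nor can it be concluded that incidence will go unreported: SAP section 1.0 places the table and listing templates in a separate document that was not available, and it may contain an incidence table. The effect of the per-protocol restriction is unknown.

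The change should be made before the final analysis. The endpoint is secondary and descriptive in an unpowered study, so this is not a critical fault.

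**What to change.** In SAP section 8.6.5:

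- **Main ADA summary.** Report the number and percentage of subjects with treatment-emergent ADA, defined as baseline negative with at least one post-dose positive through Day 365, using the validated assay's positive/negative call. Give exact 95% CIs by dose cohort and for pooled placebo, and for each antibody where results are reported separately. Pooling matters: 0/2 in a single cohort's placebo arm has an upper bound of 1 − 0.025^(1/2) = 84.2%.
- **Population.** Use the safety population as treated. The percentage denominator is dosed subjects with at least one post-dose ADA result; show the full safety N beside it.
- **Special cases.** Report baseline-positive subjects separately, including any post-dose titre rise by a pre-stated fold criterion. Show subjects with no baseline ADA result as their own row.
- **Derivation.** Add ADA status to Table 3.
- **Titres.** Keep GMT and GMFR as a secondary summary, with a stated value for negative samples. Make the per-protocol analysis supportive.

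If the table shells already hold such a display, bring its definition and population into the SAP text. The cost is SAP wording, one derived variable and a few extra table displays. No new samples are needed.
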